Latent Aging Mechanisms in Pain and Sleep (LAMPS)

ClinicalTrials.gov Identifier: NCT04683640

Date: 5/10/2022

1. Project Title

Sleep, Pain, and Aging: Potential Underlying Mechanisms (Latent Aging Mechanisms in Pain and Sleep — **LAMPS** Study)

2. Investigators:

[name] (PI)
[name] [name] (PI Proxy)
[name] [name] (Co-I)
[name] (Co-I)
[name] (Co-I)
[name] (Co-I)
[name]-PhD (Co-I)

3. Abstract:

Chronic pain is a serious public health problem peaking at older age depending on the pain condition [1]. Similarly, the capacity to sleep properly changes with age with nearly half of older adults complaining of difficulty sleeping [2][3]. Although the bidirectional link between sleep and pain is widely established, the common underlying neurobiological mechanisms have yet to be fully elucidated, especially in aging. As currently available sleep and chronic pain therapies are only partially effective, novel treatment approaches are urgently needed. Given the potential mechanistic role of GABA in both conditions, based on our preliminary data and the availability of GABA supplements over the counter, the present proposal will determine the effect of oral GABA administration in sleep quality and pain in middle to older aged adults with chronic pain and sleep disorders as well as to characterize the potential neurobiological mechanisms involved in both conditions. Results from the present investigation using a parallel, double-blinded, placebo-controlled study will provide novel and the preliminary information needed for future translational pain and sleep research.

4. Background:

Chronic pain is a serious public health problem affecting all age groups peaking at older ages depending of the pain condition [1]. Similarly, the capacity to sleep properly changes with age with nearly half of older adults complaining of difficulty sleeping, changes which start around middle age [2][3]. Although the bidirectional link between sleep and pain is widely established, the common underlying neurobiological mechanisms have yet to be fully elucidated, especially in aging. As currently available sleep and chronic pain therapies are only partially effective, novel treatment approaches targeting shared potential mechanisms underlying both conditions simultaneously are urgently needed.

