We propose a double-blinded, randomized parallel group study that will randomize older adults with musculoskeletal pain and poor sleep quality to oral self-administration of either GABA (two 250mg capsules for a total of 500mg daily) or Placebo during four weeks. Our study design was guided by recommendations by the IMMPACT group for clinical pain trials [23][24][25][26] see table 1. After initial screening, eligible participants will undergo two 2.5-hour baseline sessions (health, sensory, and neuroimaging) for the collection of clinical information, QST, and brain imaging data. During the entire study, participants will wear a OURA ring to objectively measure sleep quality. During the intervention, participants will receive a phone call once a week for an assessment of adverse effects and compliance. During the last week of the intervention period, two assessment sessions will follow, these will be identical to the baseline sessions. (Figure 5.)

To reduce participant burden and exposure risk to COVID-19, the ICF may be conducted remotely via phone calls, UF Zoom and/or online (REDCap). A copy of the signed ICF will be provided to the participant.

Participants: Older adults over 45 years of age who have a smartphone and have experienced pain of at least moderate intensity (>5/10 pain intensity ratings) on more days than not during the past three months, and who also reported poor sleep quality (>5 PSQI scores) will be considered for participation. Community-based recruitment methods established in [name] lab will be utilized.

Exclusion criteria will align with study and safety requirements broadly related to GABA administration, pain and MRI : 1) serious psychiatric conditions (e.g., schizophrenia, major depression, bipolar disorder;

Table 1. Study measures consistent with core outcome domains recommended by IMMPACT- www.immpact.org

IMMPACT Core Outcome Domain	Proposed Study Measures
Pain	Verbal Descriptor Scale (VDS) WOMAC-Pain
Physical functioning	WOMAC-Physical Function
Socio-emotional functioning	BDI-II PANAS
Sleep	Pittsburgh Sleep Quality Index Berlin Questionnaire Epworth Sleepiness Scale OurA Ring Sleep Diary
Improvement and satisfaction with treatment	Multidimensional Patient Impression of Change

Symptoms and adverse events	Passive capture of spontaneously reported adverse events and symptoms, with the use of open-ended prompts

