Disposition	Detailed information regarding participant recruitment and progress throughout the trial Self-reported evaluation of blinding

[figure not shown]
2) history of alcohol/drug abuse; 3) Alzheimer, Parkinson, Epilepsy and other known intracerebral pathology and neurological conditions; 4) significant cognitive impairment as evidenced by the Modified Mini-Mental State Examination [3MS] score ≤ 77 ; 5) hospitalizations for mental health reasons in the past year; 6) chronic/current use of narcotic medications; 7) serious systemic (uncontrolled diabetes self-reported HA1C>7), (uncontrolled hypertension $> 155/90$ mm Hg) and rheumatic disorders (i.e., rheumatoid arthritis, systemic lupus erythematosus, fibromyalgia, HIV); 8) arterial hypotension; 9) digestive tract diseases; 10) major medical surgery in the past two months, history of brain surgery or any serious brain condition like aneurysm, stroke, or seizures; 11) excessive anxiety regarding protocol procedures; 12) Inability to consent for study participation; 13) Ingestion of sleep medications including those with zolpidem (Ambien and others) and eszopiclone (Lunesta and others); 14) Neuropathic pain medications including anticonvulsants and antidepressants; 15) Allergies or sensitivity to GABA or its ingredients cellulose, gelatin (capsule), magnesium silicate, vegetable stearate and silica or to the placebo or its ingredients: calcium laurate, hypromellose capsule, magnesium (citrate), microcrystalline cellulose; 16) currently taking barbiturate and benzodiazepine and baclofen; 17) MRI contraindications including large pieces of metal in the body/face/neck and claustrophobia; 18) current cancer diagnosis unless determined no evidence of disease or in remission for at least two years, and 19) pregnancy

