Participants will be instructed to talk with the investigators about any discomforts that occur during the study. If for any reason the participant reports an injury, dizziness, anxiety, drowsiness, dry mouth, balance problems, constipation, blurred vision, itchiness, irritation or stomach pain, staff will immediately advise participants to contact emergency medical, they will be referred to their doctor, or the PI will call the doctor or other health care provider.

Before beginning data collection, all study coordinators undergo standardized training on all study procedures. A detailed checklist for each data collection element is in place to ensure all study coordinators are appropriately trained and able to conduct study procedures. Research coordinators will be certified in each element of the study visit including obtaining informed consent, administering questionnaires, protecting the confidentiality of collected data, performing the test batteries. Any study coordinator who is found to not adhere to all aspects of the protocol will be required to complete additional training followed by re-certification.

All research staff complete human subjects training required by The University of Florida institutional review board (IRB) and the National Institutes of Health (NIH). This training includes education about the importance of maintaining the confidentiality of personal health information. The study principal investigators or a co-investigator will be available to answer questions that arise during the informed consent process as needed. More information about specific protective measures against risk is outlined below.

GABA oral supplement administration

Gamma-aminobutyric acid (GABA) has become widely available as a food supplement. In the United States, GABA is considered a "food constituent" and a "dietary supplement," respectively. These GABA food supplements can be purchased online via numerous websites, including webshop giants such as Amazon.com, with often very positive customer reviews. Hundreds of people report that these supplements have helped them alleviate anxiety and/or improve sleep quality, in addition to other beneficial effects.

Physiological Effects of GABA. In recent years researchers have reported several placebo-controlled studies in which GABA was administered as a food supplement to healthy participants and participants with a history of acrophobia. One study found an increase in alpha waves in healthy participants and

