increased levels of immunoglobulin A (IgA; an indicator of immune system functioning) in participants with a history of acrophobia when they were exposed to heights [50]. Another study reported reduced heart rate variability and salivary chromogranin A (CgA) during an arithmetic task compared to a control group after the administration of GABA-enriched chocolate [51]. Additionally, participants who received 50 mg of GABA dissolved in a beverage reported less psychological fatigue after completion of the task [52].

Safety of GABA oral supplement. No significant adverse events were reported in the above studies, indicating that GABA oral supplements are generally safe. Currently, there is no established dose for GABA as a dietary supplement, and doses in the literature range from 500 to 750 milligrams taken up to two times a day. As a precaution in our preliminary study, we decided to administer the lower dose of 500 mg daily.

Excluded Medical Conditions. As a precaution, we will exclude participants who take hypertension medications since GABA can reduce blood pressure levels. We will exclude participants that ingest neuropathic pain medication as well as anticonvulsants and antidepressants.

Drug-Interactions. It does not have any known drug interactions. However, we should know about any other medications or supplements participants are taking, including prescription drugs, nonprescription drugs, vitamins, and dietary or herbal supplements. Even though there are currently no known interactions, it is important to understand that gamma-aminobutyric acid supplementation has been studied very little in humans.

Placebo oral administration

This study compares an active drug (GABA) to a placebo. A placebo is an inactive substance made to look/taste like an active medicine.

Laboratory tests. Participants will have blood drawn at screening and during the post-intervention visit for both intervention periods to measure their blood chemistry. Abnormal results will be brought to the principal investigator's attention immediately. The results will be reviewed and signed by the study clinician and [name].

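### Phase 2 neither excludes current users of GABA supplements nor says how outside use is handled, which can weaken the GABA-placebo contrast

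*Combined protocol and SAP*

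**What the plan says.** The Abstract gives "the availability of GABA supplements over the counter" as part of the reason for the trial. Section 6, under GABA oral supplement administration, adds that "Gamma-aminobutyric acid (GABA) has become widely available as a food supplement" and that "Hundreds of people report that these supplements have helped them alleviate anxiety and/or improve sleep quality". The Participants paragraph for the second phase selects on pain and on sleep: those "who also reported poor sleep quality (>5 PSQI scores) will be considered for participation".

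The Phase 2 exclusion list has 19 items. Four bear on this point:
- Item 13 reads "Ingestion of sleep medications including those with zolpidem (Ambien and others) and eszopiclone (Lunesta and others" and gives no other examples.
- Item 14 covers neuropathic pain medications.
- Item 15 is the only item that names GABA, and it concerns intolerance rather than use: "15) Allergies or sensitivity to GABA or its ingredients cellulose, gelatin (capsule".
- Item 16 covers barbiturates, benzodiazepines and baclofen.

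Section 6 separately excludes people on blood-pressure medication. On supplements, the Drug-Interactions paragraph says only that "we should know about any other medications or supplements participants are taking". Nothing follows from that statement. Initial screening, Baseline Neuroimaging Assessment, Intervention Period and Data Analysis contain no rule on GABA taken outside the study.

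**The concern.** The protocol describes an easily bought product that people take for sleep, recruits people who sleep badly, and then tests that product against placebo. Followed as written, the exclusion list admits people who already take it. Nothing in the visible text says what happens if a participant starts it during the four weeks.

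Two groups matter. Prior users allocated to GABA enter with exposure already in their baseline, so the study capsules may add less. Placebo participants who begin outside GABA after baseline receive the substance being tested. Either group narrows the between-arm difference in change for sleep and pain (H2a-H2d) and for brain and plasma GABA (H3a, H3b). The plasma outcome is the most direct case, because it measures the substance the supplement contains.

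Under Power and sample size considerations, Phase 2 exists to supply effect sizes for later, larger studies. An attenuated estimate would carry over into their sample sizes.

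**Working it through.** **The plan's own figure.** Phase 2 has 28 participants, 28 / 2 = 14 per arm. It states no effect size, SD, alpha or power, so the 28 cannot be re-derived. The medium effect in the same paragraph belongs to Phase 1.

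**Who affects the contrast.** Data Analysis specifies a pre-post repeated-measures ANOVA, so the treatment effect is the difference between arms in mean change. Let δ be the true effect of the study dose in someone not otherwise exposed.

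| Participant | Contribution to change | Effect on the contrast |
|---|---|---|
| Prior user, GABA arm | between 0 and δ, depending on what the study dose adds | towards no difference |
| Starts outside GABA, placebo arm | up to δ instead of 0 | towards no difference |
| Stable prior user, placebo arm | outside use present at both visits, so about 0 | none expected |

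**Size.** Suppose a share a of the GABA arm gains nothing further and a share b of the placebo arm responds in full. Then

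difference = δ(1 - a) - δb = δ(1 - a - b).

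With one arm affected, a share c gives δ(1 - c). With unchanged variance, information goes as the square of the effect, (1 - c)²:

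| c (assumed) | effect multiplier | information retained |
|---|---|---|
| 5% | 0.95 | 0.90 |
| 1 of 14 = 7% | 0.93 | 0.86 |
| 10% | 0.90 | 0.81 |
| 20% | 0.80 | 0.64 |

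One person in each arm gives 1 - 2/14 = 0.86, and 0.86² ≈ 0.73 of the information.

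**How likely is at least one user?** The documents give no rate of use. For an assumed rate p, the chance among 14 people is 1 - (1 - p)^14: 25% at p = 2%, 51% at 5% and 77% at 10%.

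**Scale against the trial's precision.** Assume δ = 0.8 SD, two-sided alpha 0.05 and the normal approximation. One fully affected person moves the effect to 0.8 × 13/14 = 0.74 SD, and power from 56% to 50%. The shift of 0.06 SD compares with a standard error of √(2/14) = 0.38 SD.

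**Would existing procedures detect it?** Capsule counts and the daily log track the study product. Weekly calls cover side effects and compliance. Medications are recorded at both baseline visits. Plasma GABA is drawn at the visit where capsules are dispensed, with no threshold and no rule for a high value. Use might therefore be noticed, but no action is attached.

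**The case against.** **Item 13 may already cover it.** Its wording is open-ended, and someone taking GABA for sleep could be caught by it. This stands only in part. The examples are prescription hypnotics, whereas section 6 classes GABA as a food constituent and dietary supplement. Two screeners could reasonably decide differently.

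**Supplement use is meant to be known, and plasma GABA is measured before and after.** This is true, so use could be described afterwards. It does not say who is eligible or how such participants are analysed.

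**A reader might infer that every user dilutes the contrast.** The documents do not support that. Under a pre-post analysis, a stable prior user on placebo carries the same exposure at both visits and need not bias the change.

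**A reader might take the loss of information as an estimate.** It is not one. The share of users and, in the power illustration, the effect size are assumptions. The 1 - c multiplier assumes full loss, whereas a GABA-arm prior user may still gain something from the study dose. Prior users also qualified with poor sleep and pain despite their use, which makes a full response to outside GABA less certain.

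**A reader might infer that participants are never asked to abstain.** That cannot be concluded, because the consent pages were removed. Only the absence from the visible protocol text can be stated.

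**The effect is small beside the imprecision of a 28-person pilot.** This is correct for any single test. It does not remove the bias in the estimate, which is what Phase 2 is meant to deliver.

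**Conclusion.** The point holds as a gap in eligibility and conduct that should be closed; it is not a fatal flaw. The exclusion list as written admits current users of the study product, and the visible protocol has no rule for outside use on study. The expected direction is towards no difference, through GABA-arm prior users and placebo participants who start GABA. Stable placebo users are not part of the mechanism.

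The size is unknown. The retained-information figures of 0.90 to 0.64 hold only if 5% to 20% of one arm is fully affected, and neither the share nor full loss comes from the documents. What the documents do fix is the arm size, so each affected person counts for 7% of an arm.

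**What to change.** - Add current use of GABA-containing supplements to the Phase 2 exclusion list. This also settles whether item 13 applies.
- Add one question on non-study GABA use to the existing weekly compliance call, and record the answer by date.
- Prespecify a sensitivity analysis that repeats the Phase 2 analysis without participants who report such use. Keep all randomised participants in the main analysis, because use reported after allocation is not protected by randomisation.
- Have the sponsor state how on-study use is handled. Any instruction to participants about such products is for the sponsor to decide.

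The cost is one eligibility line, one question on a call already scheduled, one extra analysis run and a slightly smaller recruitment pool. The sample size of 28 does not change. Use that was never asked about cannot be recovered reliably after the participants have finished.

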Initial screening: Interested individuals will call in using the provided phone number and after the phone consent that provides the individual information about the study and if they are interested, a pre-screening will be conducted. This screening procedure will include two questions regarding general body pain, two questions regarding back pain and seven questions regarding sleep quality in the past month. Will also assess age, gender, and additional health history information, as well as a questionnaire to assess MRI eligibility. After the phone pre-screening, if participants are eligible and still interested in participation, the baseline orientation visit will be scheduled. **Baseline Health & Sensory Assessment**

Session: After receipt the signed copy of the informed consent previously obtained using REDCap, participants will provide a fasting blood sample to evaluate standard clinical parameters (Comprehensive Metabolic Panel (CMP-14) Blood Test) and a Urine sample to measure urine specific gravity, which will be reviewed by a physician to determine study continuation. For women under the age of 62, pregnancy tests will also be conducted. This session will take place in the mornings to accommodate for fasting and to control for circadian fluctuations.

Physical examination. Height and weight will be measured as well as vital signs. Participants will complete a thorough Medical and Pain History Questionnaire, including a review of bodily systems assessing the reported duration of their pain, comorbid conditions, and current medication use.

Figure 5. Study Procedures

Sleep quality will be assessed with the Pittsburgh Sleep Quality Index (PSQI) [39] and PSQI total score will be our primary sleep outcome measure. Secondary sleep measures include Berlin Questionnaire[40], Epworth Sleepiness Scale[41], PROMIS-Sleep Related Impairment Short Form 8a[47], and FOSQ-10: A Short Version of the Functional Outcomes of Sleep Questionnaire [48].

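### The numbered Phase 2 exclusion list leaves out the protocol's own rule against enrolling people who take hypertension medication

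*Combined protocol and SAP*

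**What the plan says.** Only Phase 2 gives GABA, so the point concerns Phase 2 alone.

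- **Section 6, GABA oral supplement administration, Excluded Medical Conditions.** As a precaution, "we will exclude participants who take hypertension medications since GABA can reduce blood pressure levels". No blood-pressure level or control status is attached. The next sentence reads "We will exclude participants that ingest neuropathic pain medication as well as anticonvulsants and antidepressants".
- **Second Phase of the Study, exclusion criteria.** The list opens with "Exclusion criteria will align with study and safety requirements broadly related to GABA administration, pain and MRI" and runs to 19 items. Item 7 includes "uncontrolled hypertension $> 155/90$ mm Hg" among serious systemic disorders. Item 8 is "8) arterial hypotension". Item 14 is "Neuropathic pain medications including anticonvulsants and antidepressants". The other items naming medicines that a participant takes are 6 (narcotics), 13 (sleep medications) and 16 (barbiturates, benzodiazepines, baclofen).
- **Initial screening.** The phone pre-screen is described as "two questions regarding general body pain, two questions regarding back pain and seven questions regarding sleep quality in the past month", plus age, gender, unspecified further health history and an MRI eligibility questionnaire.
- **Baseline Health & Sensory Assessment Session.** Blood and urine samples are taken, "which will be reviewed by a physician to determine study continuation". Under Physical examination, current medication use is recorded.

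**The concern.** The rule left out of the list is a safety precaution that the protocol set for itself, for a reason it states: GABA may lower blood pressure. The list is where a coordinator would naturally look to decide eligibility, and its opening sentence says it reflects GABA safety. By limiting its hypertension bar to the uncontrolled form, item 7 invites a reader of the list alone to infer that treated, controlled hypertension is acceptable. Section 6 bars the same person because they take medication.

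Two things are at stake. The first is that someone whom the protocol means to keep out could be randomised and given the study capsules. The second is the definition of the trial population. The Data and Safety Monitoring Plan requires the study end report to address whether all participants met the entry criteria, and that question has no clean answer while the criteria differ between two sections.

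**Working it through.** No formula applies, and the plan gives no figure to reproduce. The check compares the two texts and then looks for any step that would close the gap.

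**1. The 19 items against Section 6**

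| Content | List items | Count |
|---|---|---|
| Blood pressure | 7, 8 | 2 of 19 |
| Medicines the participant takes | 6, 13, 14, 16 | 4 of 19 |
| Antihypertensives | none | 0 of 19 |

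Section 6 has two medication precautions. The second (neuropathic pain medication, anticonvulsants, antidepressants) has a counterpart in item 14. The first (hypertension medication) has none. No other part of the document states it.

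**2. Who is treated differently**

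Take a candidate without hypotension who meets no other exclusion.

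| Candidate | Numbered list | Section 6 medication rule |
|---|---|---|
| No medication, at or below 155/90 | passes | passes |
| No medication, uncontrolled above 155/90 | excluded (item 7) | not addressed |
| On medication, uncontrolled above 155/90 | excluded (item 7) | excluded |
| On medication, at or below 155/90 | **passes** | **excluded** |

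The last row is the gap. The second row is no conflict, because Section 6 does not claim to replace item 7.

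**3. Steps before capsules are handed out**

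- *Phone pre-screen.* It names 2 + 2 + 7 = 11 pain and sleep questions. Medication is not named, although the unspecified health history might include it.
- *Physician review for continuation.* As written, it applies to the blood and urine samples.
- *Medication recorded or confirmed.* This happens at 3 points: Physical examination, Quantitative Sensory Testing, and the Baseline Neuroimaging Assessment, where the capsules are dispensed. The wording at the third may limit the listing to the preceding 2–4 hours. None of the 3 carries an antihypertensive rule.

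**4. Item 14 against the second sentence of Section 6**

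Item 14 joins anticonvulsants and antidepressants to neuropathic pain medications with *including*; Section 6 uses *as well as*. Under item 14, these drugs may be excluded only as neuropathic pain treatment. Under Section 6, they are excluded in their own right. Someone taking one for another reason could be classified either way.

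**The case against.** The strongest reply is that the rule is already in force. Section 6 states it as something the study will do, under a heading about excluded conditions, and the staff-training text in that section requires retraining of coordinators who do not follow every part of the protocol. The list says it aligns *broadly* with GABA safety; it does not claim to be exhaustive. Read cumulatively, item 7 catches people above the threshold and Section 6 catches people on medication, so neither sentence is wrong by itself. This stands as far as it goes: correct exclusion may already be happening, and no screening form is shown that would settle it. It does not explain why one of two adjacent precautions reached the list and the other did not.

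It is also fair to say that the count of 0 in 3 medication checks is not specific to antihypertensives. Those steps carry no exclusion rule for any drug class. The count shows that nothing downstream repairs the omission; it is not separate evidence of a fault. The Drug-Interactions paragraph in Section 6 adds that the study should know about all other medicines, including prescription drugs. That supports finding out what people take, but attaches no exclusion to it.

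Other safeguards exist: item 8, vital signs at both baseline visits, and weekly side-effect calls. They lower the risk, but none identifies antihypertensive use as a reason to exclude.

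The item 14 difference is minor. Items 1 (major depression, bipolar disorder) and 3 (epilepsy) already remove some of the people to whom it would matter.

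**Conclusion.** The concern holds and should be fixed. The list, applied as written, admits people whom the protocol's own GABA precaution excludes. It is an omission from the list; the two rules can be applied together.

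Its size in participants cannot be computed, because the documents give no rate of antihypertensive use and none is assumed here. For scale only, with 28 participants planned in two groups of 14, each person enrolled against Section 6 would be 1/28 = 3.6% of the sample and 1/14 = 7.1% of a group.

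Confidence is high that the two texts differ. Whether anyone has been or would be enrolled wrongly depends on whether staff screen from the list alone, which the documents do not show. Which text expresses the intended clinical rule is not judged here.

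**What to change.** 1. Reconcile the Second Phase exclusion list with Excluded Medical Conditions in Section 6. The study physician should decide the intended criterion. State it once and cross-reference it, or state it identically in both places.
2. In the same amendment, align item 14 with the second sentence of Excluded Medical Conditions, so that the scope for anticonvulsants and antidepressants is the same in both.
3. Tie the agreed criterion to medication information already collected before dispensing, mainly the history under Physical examination and the confirmation at Quantitative Sensory Testing.
4. Check anyone already enrolled in Phase 2 against the agreed criterion, and carry the result into the study end report's statement on entry criteria.

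The cost is a wording amendment and a review of existing records, with no new data collection. Screening yield may fall, but only if the stricter text stands and is not already being applied.
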